### **8.3 Schedule of Events**

	V1	V2	V3	V4	V5	V6	V7	V8
Procedures/Non-Procedure Description	SCR	BL	WK4	WK8	WK12	WK16	WK20	WK24
Informed Consent	X							
Medical History and Demographics	X	X						
Inclusion/Exclusion Criteria	X	X						
Prior/Concurrent Medications/Procedures	X	X	X	X	X	X	X	X
Physical Examination	X	X	X	X	X	X	X	X
Serum Pregnancy	X							
Hepatitis B & C profile. Quantiferon Gold	X							
Safety Labs	X					X		X
Urine Pregnancy Test		X	X	X	X	X	X	X
Safety / AE Assessment	X	X	X	X	X	X	X	X
Patient Reported Outcomes / Questionnaires		X	X	X	X	X	X	X
Clinical Severity / Efficacy Assessments	X	X	X	X	X	X	X	X
Pharmacy Dispense/Drug Accountability			X	X	X	X	X	X

## 7. APPENDICES

### Appendix A

### INVESTIGATOR'S GLOBAL ASSESSMENT OF PRURIGO NODULARIS: ACTIVITY AND STAGE

Score	Category	Description: Activity (IGA PN-A)
0	Clear	No nodules have excoriations or crusts

1	Almost Clear	Very small proportion of nodules have excoriations or crusts (up to approximately 10% of all nodules)
2	Mild	Minority of nodules have excoriations or crusts (approximately 11-25% of all nodules)
3	Moderate	Many nodules have excoriations or crusts (approximately 26-75% of all nodules)
4	Severe	Majority of nodules have excoriations or crusts (approximately 26-75% of all nodules)

Score	Category	Description: Stage (IGA PN-S)
0	Clear	No nodules (0 nodules)
1	Almost Clear	Rare, flattened lesions, with no more than 5 dome-shaped palpable nodules (approximately 1-5 nodules)
2	Mild	Few, mostly flattened lesions, with small number of dome-shaped palpable nodules (approximately 6-19 nodules)
3	Moderate	Many lesions, partially flattened, and dome-shaped palpable nodules (approximately 20-100 nodules)
4	Severe	Abundant lesions, majority are dome-shaped palpable nodules (over 100 nodules)

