### **5.6.6 Investigator's Global Assessment for Prurigo Nodularis (IGA-PN)**

IGA-PN will be determined for all subjects at all visits during the study. Investigator's global assessment for prurigo nodularis (IGA PN) is a clinician-reported outcome that allows clinicians to assess the activity of PN (IGA PN-A) using a 5-point scale from 0 (clear) to 4 (severe); and the stage of the disease (IGA PN-S) using a 5-point scale from 0 (clear) to 4 (severe). [See Appendix A](#)

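### Appendix A prints the same range (about 26-75% of nodules) for IGA PN-A scores 3 and 4 and none above 75%, so percent improvement in PN-A depends on an unstated cut-point

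*Combined protocol and SAP*

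**What the plan says.** Section 5.6.6 states that "IGA-PN will be determined for all subjects at all visits during the study" and that clinicians use it to "assess the activity of PN (IGA PN-A) using a 5-point scale from 0 (clear) to 4 (severe". It refers them to Appendix A and adds no boundaries of its own. The schedule in section 8.3 marks efficacy assessments at all eight visits.

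The PN-A rows above Clear in Appendix A are:

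- Score 1: "Very small proportion of nodules have excoriations or crusts (up to approximately 10% of all nodules".
- Score 2: "Minority of nodules have excoriations or crusts (approximately 11-25% of all nodules".
- Score 3: "Many nodules have excoriations or crusts (approximately 26-75% of all nodules".
- Score 4: "Majority of nodules have excoriations or crusts (approximately 26-75% of all nodules".

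The PN-S table in the same appendix shows how such a scale normally closes. Its score 3 is "Many lesions, partially flattened, and dome-shaped palpable nodules (approximately 20-100 nodules" and its score 4 is "Abundant lesions, majority are dome-shaped palpable nodules (over 100 nodules".

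The Synopsis (Study Endpoints) and section 8.2 list percent improvement in PN-S and PN-A at Weeks 12 and 24 as a secondary endpoint. Neither gives a formula.

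**The concern.** Scores 3 and 4 share one numeric range, and nothing is printed above 75%. The lower PN-A rows abut, and the PN-S rows abut and end open-ended, so the top of the PN-A scale is the exception. No other section corrects it.

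A rater whose patient has excoriations or crusts on 60% of nodules can defend either score from the sheet. Scores 3 and 4 enter percent improvement in PN-A, so the reported result depends on a cut-point that the plan does not state. Consistent rating does not remove the problem: two raters who each apply their own rule without error can report different improvement for identical skin. A reader of the results could not tell what a PN-A of 3 or 4 meant. All 25 subjects receive upadacitinib, so there is no comparator rated on the same sheet.

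**Working it through.** The plan gives no derived figure to reproduce. The check maps percentages to the printed rows and then follows the scores into the endpoint.

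**Inputs.** The PN-A rows are from Appendix A, taking score 0 as 0% of nodules. The sample size of 25 is from section 8.2.

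**Coverage by number.** Of the 101 whole percentages from 0 to 100:

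- 0-25 (26 values) each fit one score.
- 26-75 fit both 3 and 4: 75 - 26 + 1 = 50 values.
- 76-100 fit no score: 100 - 76 + 1 = 25 values.

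**What the words add.** At 26-50%, *Majority* conflicts with its own printed range, so the words favour score 3. Above 75%, *Majority* and the category Severe favour score 4, although the number has to be set aside. At about 51-75%, both rows fit in word and number.

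**Effect on one patient.** Assume percent improvement = 100 x (baseline - follow-up)/baseline. Compare two rules, each applied consistently: Rule A scores 4 above 50% (from the word), and Rule B scores 4 above 75% (from the table's gap). Lower rows are as printed.

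| Nodules affected, baseline to follow-up | Rule A | Rule B | A - B (points) |
|---|---|---|---|
| 60% to 20% | (4-2)/4 = 50.0% | (3-2)/3 = 33.3% | 16.7 |
| 60% to 8% | (4-1)/4 = 75.0% | (3-1)/3 = 66.7% | 8.3 |
| 60% to 40% | (4-3)/4 = 25.0% | (3-3)/3 = 0% | 25.0 |
| 80% to 60% | (4-4)/4 = 0% | (4-3)/4 = 25.0% | -25.0 |
| 60% to 0% | (4-0)/4 = 100% | (3-0)/3 = 100% | 0 |
| 80% to 20% | (4-2)/4 = 50.0% | (4-2)/4 = 50.0% | 0 |
| 40% to 60% | (3-4)/3 = -33.3% | (3-3)/3 = 0% | -33.3 |
| 60% to 80% | (4-4)/4 = 0% | (3-4)/3 = -33.3% | 33.3 |
| 20% to 60% | (2-4)/2 = -100% | (2-3)/2 = -50% | -50 |
| 8% to 60% | (1-4)/1 = -300% | (1-3)/1 = -200% | -100 |

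For patients who do not worsen, the difference is at most 25 points, in either direction. For those who worsen it can be larger. A low baseline PN-A is possible because section 5.2.1 admits subjects by lesion count, not by PN-A.

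**If the number is followed instead of the word.** Rules A and B agree at 26-50%. A rater who follows the printed number could score 4 there as well. A change from 40% to 20% would then read (4-2)/4 = 50.0% rather than (3-2)/3 = 33.3%.

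**Alternative meaning of the endpoint.** For the Week 24 itch endpoint, section 8.2 speaks of percent improvement where the Synopsis speaks of a proportion of patients. The PN-A endpoint may therefore mean the share of patients who improve. On that reading, 60% to 20% and 60% to 8% count as improved under both rules. But 60% to 40% counts only under Rule A, and 80% to 60% only under Rule B. Each such patient moves the result by 1/25 = 4 percentage points.

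**Inconsistent rating.** Unchanged skin scored 4 then 3 reads (4-3)/4 = +25.0%; scored 3 then 4, it reads (3-4)/3 = -33.3%.

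**The case against.** The best defence is that this is one duplicated number, probably a copying slip. The ranges are approximate, and the words steer a sensible rater to score 4 at the top of the scale and to score 3 below one half. Only one of several secondary endpoints is touched, in an exploratory single-arm study of 25 subjects, so no between-arm comparison can be biased. Every per-patient figure above rests on an assumed formula or an assumed reading of the endpoint.

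Most of this stands, and it limits the weight of the point. It does not settle the range of about 51-75%, where word and number both allow either score. The defect also survives both readings of the endpoint, though on the second only where the result turns on a change between 3 and 4. A fault in the table's layout is unlikely to explain it, since the two rows are complete and differ in their words.

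A reader might infer more: that the trial's efficacy result is unsound, or that PN-A improvement will be inflated. The documents support neither. The primary endpoint is WI-NRS; PN-S and DLQI do not use these rows; PN-A 0/1 depends on the rows for 0, 1 and 2, which do not overlap; and eligibility is by lesion count. The direction also varies, since Rule A gives more improvement for 60% to 40% and less for 80% to 60%. With no PN-A distribution given, any figure for the group would be invented. A reader might also infer that everything above 25% is unscorable, but that ignores the words, which point one way at 26-50% and above 75%.

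**Conclusion.** The point holds as an internal inconsistency in a scoring sheet that the trial relies on, with limited reach. The top two PN-A rows cannot both be right as printed, and nothing else in the documents states the boundary.

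Under the assumed formula and the two rules compared, the same skin can differ by up to 25 points in reported improvement if it does not worsen, and by more if it does (100 points for 8% to 60%). If the endpoint is the share of patients who improve, each patient whose result turns on the 3/4 boundary is worth 4 percentage points. The size and direction of any effect on the group result cannot be derived. The absence of a formula is a separate gap, but correcting the rows is needed whichever formula applies.

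**What to change.** Reconcile the score 3 and score 4 rows with the source instrument, in words as well as numbers, so that the PN-A ranges do not overlap and together cover 0-100%. The table's gap suggests above about 75% for score 4, but this must be confirmed. If it is right, *Majority* needs checking too, because it also describes 51-75%. Reissue the sheet before the first rating.

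If rating has begun, keep the scores as recorded, do not rescore with outcomes known, and state in the report which ratings used the uncorrected sheet. That statement matters because a change of sheet can itself move a score: unchanged skin at 51-75%, scored 4 on the printed sheet and 3 on one cut at about 75%, reads +25%.

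The cost is a two-row table correction, one check against the instrument and, if needed, a note in the report covering at most 25 x 3 = 75 endpoint ratings (baseline, Weeks 12 and 24).

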## Appendix B

### WI-NRS

1. Numerical Rating Scale. On a scale from 0 (no itch) to 10 (worst imaginable itch)...

...how was your itch, on average, within the past 24 hours? Please select one number.

0    1    2    3    4    5    6    7    8    9    10

...how was your worst itch in the past 24 hours? Please select one number.

0    1    2    3    4    5    6    7    8    9    10

## Appendix C

### Dermatology Life Quality Index

#### **DERMATOLOGY LIFE QUALITY INDEX**

**DLQI**

Hospital No:

Date:

Name:

Score:

Address:

Diagnosis:

**The aim of this questionnaire is to measure how much your skin problem has affected your life OVER THE LAST WEEK. Please tick  one box for each question.**

1. Over the last week, how itchy, sore, painful or stinging has your skin been?	Very much 
	A lot 
	A little 
	Not at all 
2. Over the last week, how embarrassed or self conscious have you been because of your skin?	Very much 
	A lot 
	A little 
	Not at all 
3. Over the last week, how much has your skin interfered with you going shopping or looking after your home or garden ? relevant 	Very much 
	A lot 
	A little 
	Not at all  Not
4. Over the last week, how much has your skin influenced the clothes you wear? relevant 	Very much 
	A lot 
	A little 
	Not at all  Not
5. Over the last week, how much has your skin affected any social or leisure activities? relevant 	Very much 
	A lot 
	A little 
	Not at all  Not
6. Over the last week, how much has your skin made it difficult for you to do any sport ? relevant 	Very much 
	A lot 
	A little 
	Not at all  Not
7. Over the last week, has your skin prevented you from working or studying ? relevant 	Yes 
	No  Not

If "No", over the last week how much has your skin been a problem at **work or studying?**

A lot   
A little   
Not at all

**8.** Over the last week, how much has your skin created problems with your **partner** or any of your **close friends** or **relatives?**  
relevant

Very much   
A lot   
A little   
Not at all  Not

**9.** Over the last week, how much has your skin caused any **sexual difficulties?**  
relevant

Very much   
A lot   
A little   
Not at all  Not

**10.** Over the last week, how much of a problem has the **treatment** for your skin been, for example by making your home messy, or by taking up time?  
relevant

Very much   
A lot   
A little   
Not at all  Not

**Please check you have answered EVERY question. Thank you.**

©AY Finlay, GK Khan, April 1992 [www.dermatology.org.uk](http://www.dermatology.org.uk), this must not be copied without the permission of the authors.
